#### 8.1 Ixazomib

8.1.1 Description

The chemical name is: B-[(IR)-1-[[2-[(2,5-dichlorobenzoyl)amino]acetyl]amino]-3methylbutyl]boronic acid. Ixazomib, also known as MLN9708 and Ninlaro, is an oral proteasome inhibitor. The molecular formula is C20H23BCl2N2O9. The molecular weight is 517.12.

#### 8.1.2 Form

Ixazomib is provided by Millennium in capsule form as outlined in the table below:

| Dose     | Capsule Size | Capsule Color |  |  |
|----------|--------------|---------------|--|--|
| Strength |              |               |  |  |
| 4.0 mg   | Size 4       | Ivory         |  |  |
| 3.0 mg   | Size 3       | Light gray    |  |  |
| 2.3 mg   | Size 2       | Light pink    |  |  |

The capsules are individually packaged using cold-form foil-foil blisters that are in a child-resistant carton. There are 3 capsules in each wallet/carton.

#### 8.1.3 Storage and Stability

Upon receipt at the investigative site, ixazomib should remain in the blister and carton provided until use or until drug is dispensed. The container should be stored at the investigative site as directed on the label. Do not store about 30°C. Do not freeze. Ensure that the drug is used before the retest expiry date provided by Millennium. Expiry extensions will be communicated accordingly with updated documentation to support the extended shelf life.

In countries where local regulations permit, ixazomib capsules dispensed to the patient for takehome dosing should remain in the blister packaging and refrigerated as noted above until the point of use. The investigative site is responsible for providing the medication to the patient in the correct daily dose configurations. Comprehensive instructions should be provided to the patient in order to ensure compliance with dosing procedures. Patients who are receiving take-home medication should be given only 1 cycle of medication at a time, unless in maintenance, when they may receive 3 cycles worth. Patients should be instructed to store the medication as directed on the label for the duration of each cycle. Do not store above 30°C. Do not freeze. Patients should be instructed to return their empty blister packs to the investigative site, rather than discarding them. Reconciliation will occur accordingly when the patient returns for their next cycle of take-home medication. Any extreme in temperature should be reported as an excursion and should be dealt with on a case-by-case basis.

#### 8.1.4 Handling

Because ixazomib is an investigational agent, it should be handled with due care. Patients should be instructed not to chew, break, or open capsules. In case of contact with broken capsules, raising dust should be avoided during the clean-up operation. The product may be harmful by inhalation, ingestion, or skin absorption. Gloves and protective clothing should be worn during cleanup and return of broken capsules and powder to minimize skin contact.

The area should be ventilated and the site washed with soap and water after material pick-up is complete. The material should be disposed of as hazardous medical waste in compliance with federal, state, and local regulations.

In case of contact with the powder (eg, from a broken capsule), skin should be washed immediately with soap and copious amounts of water for at least 15 minutes. In case of contact with the eyes, copious amounts of water should be used to flush the eyes for at least 15 minutes. Medical personnel should be notified. Patients are to be instructed on proper storage, accountability, and administration of ixazomib, including that ixazomib is to be taken as intact capsules.

#### 8.1.5 Availability

The study drug ixazomib capsules will be provided by Millennium free of charge. The study drug will be labeled and handled as open-label material, and packaging labels will fulfill all requirements specified by governing regulations.

#### 8.1.6 Preparation, Reconstitution, and Dispensing

Ixazomib is an anticancer drug and as with other potentially toxic compounds caution should be exercised when handling ixazomib capsules.

During Induction, 1 cycles worth of ixazomib will be provided at each cycle day 1, and patients will not be required to take doses in clinic.

During maintenance, patients may return to clinic every 3 cycles beginning with cycle 10. If this option is utilized, a 3 month supply of ixazomib will be supplied by the investigational pharmacy at each visit.

Patients are to be instructed on proper storage, accountability, and administration of ixazomib, including that ixazomib is to be taken as intact capsules.

#### 8.1.7 Administration

Ixazomib will be given daily on days 1, 8, and 15 of each 28 day cycle on an out-patient basis.

At all times when dispensing ixazomib protocol therapy, study site personnel will review the instructions, printed on the packaging, with participants.

Patients should be instructed to swallow ixazomib capsules whole, with water, and not to break, chew, or open the capsules. Study drug should be taken on an empty stomach (no food or drink) at least 1 hour before or 2 hours after a meal. Each capsule should be swallowed separately with a sip of water. A total of approximately 8 ounces (240 mL) of water should be taken with the capsules.

#### 8.1.8 Ordering

The investigator or designee will order ixazomib from Millennium, according to the ordering instructions provided by company.

#### 8.1.9 Accountability

Study drug will be administered or dispensed only to eligible patients under the supervision of the investigator or identified sub-investigator(s). The appropriate study personnel will maintain records of study drug receipt and dispensing.

#### 8.1.10 Destruction and Return

Investigational ixazomib (expired or end of study) should be destroyed on site according to the institution's standard operating procedure. Be sure to document removal and destruction on drug accountability logs.

#### 8.2 Lenalidomide

8.2.1 Description

Lenalidomide (REVLIMID®), a thalidomide analogue, is an immunomodulatory agent with antiangiogenic properties. The chemical name is 3-(4-amino-1-oxo 1,3-dihydro -2H- isoindol-2-yl) piperidine-2,6-dione and it has the following chemical structure: 3-(4-amino-1-oxo 1,3-dihydro-2H-isoindol-2-yl) piperidine-2,6-dione. The empirical formula for lenalidomide is C13H13N3O3, and the gram molecular weight is 259.3.

#### 8.2.2 Form

Lenalidomide is off-white to pale-yellow solid powder. It is soluble in organic solvent/water mixtures, and buffered aqueous solvents. Lenalidomide is more soluble in organic solvents and low pH solutions. Solubility was significantly lower in less acidic buffers, ranging from about 0.4 to 0.5 mg/ml. Lenalidomide has an asymmetric carbon atom and can exist as the optically active forms S(-) and R(+), and is produced as a racemic mixture with a net optical rotation of zero.

Lenalidomide is available for this study as 5 and 25 mg capsules for oral administration. Each capsule contains lenalidomide as the active ingredient and the following inactive ingredients: lactose anhydrous, microcrystalline cellulose, croscarmellose sodium, and magnesium stearate.

#### 8.2.3 Storage and Stability

At the study site, all investigational study drugs will be stored in a locked, safe area to prevent unauthorized access. Lenalidomide should be stored at room temperature away from direct sunlight and protected from excessive heat and cold.

#### 8.2.4 Handling

Females of childbearing potential should not handle or administer lenalidomide unless they are wearing gloves.

Qualified personnel, familiar with procedures that minimize undue exposure to themselves and the environment, should undertake the preparation, handling, and safe disposal of the chemotherapeutic agent in a self-contained and protective environment.

#### 8.2.5 Availability

Celgene Corporation will supply Revlimid® (lenalidomide) to study participants at no charge through Celgene's Revlimid Risk Evaluation and Mitigation StrategyTM (REMS) (formerly known as RevAssist® Program, Research). Each patient's individual drug supply will be delivered to the

Local Protocol #: 16-313 Version Date: 04 October2019

site by the drug courier Biologics and be distributed to the patient through the research side of the pharmacy of that site.

Further information about the Revlimid REMS® program is available at www.celgeneriskmanagement.com.

8.2.6 Preparation

Lenalidomide is an oral drug, and does not require specific preparation details.

#### 8.2.7 Administration

Lenalidomide will be given daily on days 1-21 of each 28 day cycle At all times when dispensing lenalidomide protocol therapy, study site personnel will review the instructions, printed on the packaging, with participants.

#### 8.2.8 Ordering

Lenalidomide (Revlimid®) will be provided to research subjects for the duration of their participation in this trial at no charge to them or their insurance providers. Lenalidomide will be provided in accordance with the Celgene Corporation's Revlimid REMS® program. Per standard Revlimid REMS® program requirements, all physicians who prescribe lenalidomide for research subjects enrolled into this trial, and all research subjects enrolled into this trial, must be registered in, and must comply with, all requirements of the Revlimid REMS® program.

Drug will be shipped on a per patient basis by the contract pharmacy to the clinic site.

#### Only enough lenalidomide for one cycle of therapy will be supplied to the patient each cycle.

Lenalidomide will be shipped directly to the clinic site. Bottles will contain a sufficient number of capsules for one cycle of dosing.

During maintenance, patients may return to clinic every 3 cycles beginning with cycle 10. If this option is utilized, lenalidomide may be shipped from the investigational pharmacy to the patient's home for each cycle the patient does not return to clinic, according to local practice.

#### 8.2.9 Accountability

The Investigator or designee is responsible for taking an inventory of each shipment of study drug received, and comparing it with the accompanying study drug accountability form.

#### 8.2.10 Destruction and Return

If study drugs (those supplied by the sponsor or sourced by the investigator) are to be destroyed on site, it is the investigator's responsibility to ensure that arrangements have been made for the disposal, procedures for proper disposal have been established according to applicable regulations, guidelines and institutional procedures, and appropriate records of the disposal have been documented. The unused study drugs should be destroyed per institutional policies. If any study drug is lost or damaged, its disposition should be documented in the source documents. Patients will be instructed to return empty bottles or unused capsules to the clinic site.

#### 8.3 Dexamethasone

#### 8.3.1 Description

Dexamethasone is a synthetic adrenocortical steroid. Corticosteroids are naturally occurring chemicals produced by the adrenal glands located above the kidneys. Corticosteroids affect the function of many cells within the body and suppress the immune system. Corticosteroids also block inflammation and are used in a wide variety of inflammatory diseases affecting many organs.

The molecular weight for dexamethasone is 392.47. It is designated chemically as 9- fluoro- $11\beta$ , 17, 21-trihydroxy-16 $\alpha$ -methylpregna-1, 4-diene-3, 20-dione. Dexamethasone is stable in air and almost insoluble in water.

#### 8.3.2 Form

Dexamethasone is a white to practically white, odorless, crystalline powder. It is available in 2 or 4 mg tablets (commercially) for oral administration. Each tablet contains dexamethasone as the active ingredient, and the following inactive ingredients: calcium phosphate, lactose, magnesium stearate, and starch. The tablet shell may contain the following: D&C Yellow 10, FD&C Yellow 6, and/or FD&C Blue 1.

#### 8.3.3 Storage and Stability

At the study site, all investigational study drugs will be stored in a locked, safe area to prevent unauthorized access. Dexamethasone should be stored at controlled room temperature, 68-77°F (20-25°C) and not frozen, and according to label requirements.

#### 8.3.4 Handling

Dexamethasone should be handled by trained pharmacy staff. The use of gloves and other appropriate protective clothing is recommended as necessary.

#### 8.3.5 Availability

Dexamethasone supply will be obtained through commercial supply.

#### 8.3.6 Preparation

Dexamethasone is an oral drug, and does not require specific preparation details.

#### 8.3.7 Administration

During induction therapy, participants will receive dexamethasone as a single oral daily dose on Days 1, 8 and 15 and 22 of cycles 1-9.

#### 8.3.8 Ordering

Dexamethasone will be ordered from retail pharmacy using commercial drug supply.

8.3.9 Accountability

As drug is from commercial supply, sites should keep records per their institutional policies.

8.3.10 Destruction and Return

At the end of the study, unused supplies of dexamethasone should be destroyed and documented according to institutional policies.

#### 9. BIOMARKER, CORRELATIVE, AND SPECIAL STUDIES

This trial will provide samples SMM patients treated with Ixazomib, lenalidomide and dexamethasone to comprehensively characterize the MM genome and immune cells function and define molecular events driving development and progression of MM. Please see Appendix D for a listing of further proposed correlative studies.

We will attempt to obtain samples on all patients who consent to the optional studies at the following time points: before therapy, at the end of cycle 9 or at the time of response confirmation if prior to Cycle 9, at the time of response determination (CR), and at disease relapse, and at the time of completion of the study. It is anticipated that approximately 90% of samples collected will be adequate for sequencing studies proposed. Participants may decline sample collection at any timepoint.

The tumor cells will be collected as described below. From these samples, high quality DNA (for tumor cells) and RNA (for tumor cells and immune cells) for both exome sequencing and RNA sequencing will be obtained. Germline DNA will be also obtained from a buccal swab from all patients at any time point of the study.

Peripheral blood and bone marrow derived mononuclear cells will undergo immunologic assessments to assess the impact of therapy on general measures of cellular immunity, MM reactive T cells, and antigen specific immunity. The percentage of circulating and bone marrow derived regulatory immune cells will be determined.

Peripheral blood and bone marrow samples will be collected per the collection time described in the table of sample collection. Minimum residual disease (MRD) will be assessed as standard of care at the time of CR or VGPR by Adaptive using spiked-in reference sequences. Clinical bone marrow aspirate samples should be collected per institutional guidelines and sent to Adaptive for analysis.

Single-cell sequencing will be performed on patients prior to treatment and at the end of induction.

Participants either identified as responders, or non-responders will have an additional timepoint sequenced, to be determined, after review of response to therapy. All single-cell Droplet RNA sequencing (Drop-seq) will be performed by the Broad Institute. We will first use drop-seq of CD138+ cells and CD138-ve CD45+ or CD138-ve CD45-ve cells from viably frozen cells in DMSO.

#### 9.1 Bone Marrow Aspirate Samples

Collection of bone marrow aspirate specimens for exploratory analysis will be obtained at the times of bone marrow collections. Specimens will be shipped (via traceable carrier) to and subsequently processed, analyzed, and stored at Dana-Farber Cancer Institute.

Specimens Required: 2 x 10mL Purple Top Tubes (K2EDTA). Specimens must be collected on Mondays to Thursdays for same-day shipment.

Processing Information: There is no required processing for bone marrow samples at each participating site prior to shipment.

Shipping Information for Bone Marrow Aspirate Specimens: Label all specimens with the following: Subject Initials, Subject study number (will include protocol number), Visit at which sample was drawn (screening, response or relapse/progression), Date sample drawn (mm/dd/yyyy), Time sample drawn (24 hour clock).

9.1.1 Shipping Instructions:

#### Shipments must be sent on the day of collection and cannot be batched.

- 1. An inventory sheet including a complete list of samples shipped (patient number, timepoint, study #) must accompany each shipment. Please sign and date the form, and
- 2. An electronic copy (Word or Excel) of the sample list must also be sent via email. The listing must also include a contact name, address and phone number of the person who is responsible for the shipment.
- 3. Please email shipment.

to notify of an incoming

Please ship Monday to Thursday as shipments cannot be received on weekends and/or on holidays.

4. Once drawn, samples may be shipped via overnight air to:

Please retain a copy for site record maintenance. Please see Appendix C and D for Collection Schedule and Requisition Form

#### 9.2 Peripheral Blood Samples

Collection of peripheral blood specimens (including serum and plasma) for exploratory analysis will be optional for this trial, except for the screening sample, which is mandatory. Purple top and red top tube collections will be obtained at the same timepoints as bone marrow samples for correlative studies (see Section 10 for list of required timepoints, and Appendix B for specific instructions). These collections will be taken at the time of routine blood collection timepoints required for this study. Specimens will be processed on site according to instructions below and shipped (via traceable carrier) to Dana-Farber Cancer Institute. Once the shipment is received, samples will be subsequently processed, analyzed, and stored at Dana-Farber.

- 9.2.1 Specimens Required: 2 x 10 mL Purple Top Tubes (K2EDTA) and 1 x 6 mL red top tube, should be collected Mondays to Thursdays for same-day shipment.
- 9.2.2 Shipping Information: Label all specimens with the following:
  - Subject Initials, Subject study number (will include protocol number), Visit at which sample was drawn (screening, response or relapse/progression), Date sample drawn (mm/dd/yyyy), Time sample drawn (24 hour clock)
- 9.2.3 Processing Information: Once collected, the vacutainers will be refrigerated and and stored according to instructions below. There is no required processing for purple top tubes at each participating site prior to shipment.
- 9.2.4 Shipping Instructions: Shipments must be sent on the day of collection and cannot be batched.

#### **Processing Information:**

Invert each tube 5 times at blood collection to ensure adequate mixing of anticoagulant with blood immediately after the blood collection. Package tubes at room temperature and wrap in a liberal amount of paper towel around the tubes to ensure adequate insulation of the specimen(s) and absorption in the event of a breakage. Place wrapped specimen in a biohazard labeled Ziploc bag with a fridge pack and zip close. Wrap bubble wrap around the bag and place in a cardboard box. If space remains in the box, stuff with extra paper towel to reduce shifting of samples. Complete the shipping requisition form using the address listed below. Prepare the package for shipping, applying packing tape as needed. Ship the package using FedEx or UPS next day or overnight delivery the same day the sample was collected. Please only ship Monday-Thursday, as the lab is only able to accept Saturday shipments with 1 week advance notice. With each shipment, please include the following:

- 1. An inventory sheet including a complete list of samples shipped (patient number, timepoint, study #) must accompany each shipment. Please sign and date the form, and retain a copy for site record maintenance. See Appendix C for Sample Requisition Form
- 2. An electronic copy (Word or Excel) of the sample list must also be sent via email and include the tracking number of the package. The listing must also include a contact name, address and phone number of the person who is responsible for the shipment.

- 3. Please email [name] ([name]\[contact]) to notify of an incoming shipment.
- 4. Please ship Monday to Thursday as shipments cannot be received on weekends and/or on holidays.
- 5. Once drawn, samples may be shipped via overnight air to:

Please retain a copy for site record maintenance.

#### **10. STUDY CALENDAR**

Screening evaluations are to be conducted within 28 days prior to registration. If bone marrow biopsy, research aspirate, and imaging assessments are completed within 6 weeks of registration, they do not need to be repeated at screening. Baseline assessments are to be conducted on C1D1 of initial therapy. C1D1 must occur within 6 weeks of registration. If screening assessments are performed within 7 days of C1D1, disease assessments do not need to be repeated. All assessments must be performed prior to administration of any study medication. Study assessments and medications should be administered within +/- 3 days (during cycles 1-2) and +/- 7 days (during cycles 3-24) of the protocol-specified date, unless otherwise noted. See below for detailed scheduled of assessments. Study medications will be administered according to the schedule and guidelines outlined in Section 5.

|   | Pre-registration                             |  | Cycles 1-24 (28 days)       |   |   |                             | Event
Monitoring                            |
|---|--|--|---|---|---|-----------------------------|--|
| Tests and procedures  | ≤ 28
days
prior to
registrat
ion | ≤ 21
days
prior to
registrat
ion | Day 1 of
cycles 1-
9  | Every 3
months for
Cycles 10-
24 | Cycle 10
Day 1/ Or
to
confirm
CR  | End of
Tx (± 2
weeks) | Every 3
Months (±
2 weeks)  |
| History and exam, height, weight.
Performance Status   | Х  |  | Х                                       | Х   |   | Х                           | X  |
| Toxicity Notation   |  |  | Х                                       | Х   |   | Х                           |  |
| Hematology group (WBC w/ diff, PLT, Hgb, ANC)   |  | Х  | Х                                       | Х   |   | Х                           | Х  |
| Chemistry   |  | Х  | Х                                       | Х   |   | Х                           | Х  |
| Direct & total bilirubin    |  | Х  | Х                                       | Х   |   | Х                           |  |
| Free light chain assay  |  | Х  | Х                                       | Х   |   | Х                           | Х  |
| Serum and Urine Immunofixation
(SPEP and UPEP) with quantitative
immunoglobulins  |  | Х  | Х                                       | Х   |   | Х                           | X  |
| β2M and LDH   |  | Х  | Х                                       | Х   |   | Х                           |  |
| Metastatic Bone Survey and MRI of
the Full Spine
OR
PET/CT      | Х  |  |   |   |   | Х                           |  |
| EKG   |  | Х  |   |   |   | Х                           |  |
| Serum or urine pregnancy test    |  | Х  | Х                                       |   |   |                             |  |
| Unilateral bone marrow aspirate and biopsy    | Х  |  |   |   | Х   | Х                           |  |
| Research bone marrow aspirate   | X                                |  |   |   | X   | X               |  |
| Research Blood    | X                                |  | X                           | X                             | X   | X               |  |
| Buccal Swab    | Х  |  |   |   |   |                             |  |

1- Cycle 1, Day 1 laboratory values need to meet eligibility criteria

2- Direct bilirubin to be obtained if total bilirubin is abnormal

3- Scheduling allows for +/- 3 days cycles 1-2 and +/- 7 days for cycle 3 and beyond

4- Chemistry includes sodium, potassium, chloride, bicarbonate, bun, creatinine, calcium, glucose, albumin, ALT (SGPT), total protein, AST (SGOT), total bilirubin, magnesium, and phosphorus

5- These procedures should also be done at any time during the course of the study to confirm CR Aspirate should be collected and sent out to Adaptive for MRD analysis at baseline and at time of VGPR or suspected CR

6- Research bone marrow aspirate and biopsy at the same time of clinically indicated bone marrow biopsy and to confirm response

7- Peripheral blood samples for correlative studies

8- If BM biopsy performed within 3 weeks of C10D1, or confirmation of CR BM biopsy performed within 3 weeks of stem cell collection, do not need to repeat BM biopsy

9- If the participant's disease response is not followed primarily via a UPEP and Urine immunofixation, these tests may be done only at screening, end of treatment, and as clinically indicated during treatment and follow-up

10-The buccal swab can be performed at any timepoint during study participation

11-Pregnancy tests are only required for women of childbearing potential 10-14 days prior to registration, 24 hours prior to prescribing lenalidomide for C1 and every day 1 post C1

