#### **1.4 Duration of Study**

A treatment cycle is defined as 28 consecutive days.

Patients will receive 9 cycles of induction therapy followed by 15 cycles of maintenance therapy for a total of 24 months.

For treatment cycles 1 and 2, a +/-3 day window is allowed. For treatment cycles 3 through 24, a +/-7 day window is allowed. Treatment plan is designed to be administered on an outpatient basis, however if necessary, may be given as inpatient.

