## Treatment may not begin without confirmation from the Coordinating Center that the participant has been registered.

### NOTE: Same day treatment registrations will only be accepted with prior notice and discussion with DFCI.

#### 5. TREATMENT PLAN

#### 5.1 Treatment Regimen

Treatment will consist of 9 cycles of induction therapy followed by maintenance therapy for a total of 24 months. A treatment cycle is defined as 28 consecutive days.

For treatments cycle 1 and 2, a +/- 3 day window is allowed. For treatments cycle 3 through 24 a +/-7 day window is allowed.

No investigational or commercial agents or therapies other than those described below may be administered with the intent to treat the participant's malignancy.

| Agent         | Pre-medications/
Precautions                              | Dose  | Route | Schedule                   | Cycle
Length |
|---------------|--|-------|-------|----------------------------|-----------------|
| Ixazomib      | Should not be taken with food                                | 4 mg  | Oral  | Days 1, 8, 15              |                 |
| Lenalidomide  | None   | 25 mg | Oral  | Days 1–21 of
each cycle | 28 days         |
| Dexamethasone | Take with food;
Recommended to be
taken in the morning | 40 mg | Oral  | Days 1, 8, 15, 22          | -               |

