#### 5.2.2 Lenalidomide

Lenalidomide will be given as a single daily oral dose of 25 mg per day on days 1–21 followed by a 7-day rest period for cycles 1–9 and 15 mg per day on days 1-21 for cycles 10–24. A window of +/-7 days is allowed, except cycles 1 and 2 which will be +/-3 days. Dose modification guidelines are described in Section 6.2 (Dose Modifications/Delays).

Lenalidomide capsules should be swallowed whole, and should not be broken, chewed or opened. Administration of lenalidomide will be at approximately the same time each day. Drug may be taken with or without food. If a dose is missed and less than 12 hours has elapsed since the missed dose, the patient can take the dose for that day. If more than 12 hours has elapsed since missing a dose at the normal time, the patient should not take the dose, but take the next dose at the normal time on the following day. If a dose is missed, it should be taken as soon as possible on the same day. If a dose is vomited, the dose should not be made up and the participant should continue with the regular schedule of the drug at the next dose. A drug diary will be provided to participants to record oral administration of doses.

Participants who take more than the prescribed dose of lenalidomide should be instructed to seek emergency medical care if needed and contact study staff immediately. Participants experiencing adverse events may need study treatment modifications (see Section 6.2).

Lenalidomide related resources will be provided to all patients prior to receiving lenalidomide therapy as part of the Revlimid REMS program. For more information regarding program registration and drug ordering, refer to section 8.2.

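### The two-sided dosing window lets a cycle start up to 7 days early, which can remove the whole lenalidomide rest week

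*Combined protocol and SAP*

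**What the plan says.** **The window.** Section 10 sets it for assessments and drugs together: "Study assessments and medications should be administered within +/- 3 days (during cycles 1-2) and +/- 7 days (during cycles 3-24", counted from a date described only as "of the protocol-specified date, unless otherwise noted". Section 1.4 repeats it ("For treatment cycles 3 through 24, a +/-7 day window is allowed"), as do Section 5.1 ("For treatments cycle 3 through 24 a +/-7 day window is allowed") and footnote 3 of the Study Calendar. Section 5.2.2 places it in the lenalidomide dosing paragraph itself: "A window of +/-7 days is allowed, except cycles 1 and 2 which will be +/-3 days".

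**The schedule.** Section 5.1 says "A treatment cycle is defined as 28 consecutive days". For cycles 1-9, Section 5.2.2 gives lenalidomide on days 1-21, "followed by a 7-day rest period". For later cycles the rest is implied by Section 8.2.7: "Lenalidomide will be given daily on days 1-21 of each 28 day cycle". Ixazomib is given on days 1, 8 and 15 (Sections 5.1 and 8.1.7). Dexamethasone is given on days 1, 8, 15 and 22 in cycles 1-9 (Section 5.2.3).

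Nowhere is the window limited to delays, and nowhere is a minimum interval given between one Day 1 and the next. Section 10 refers to Section 5 for drug administration, but Section 5 repeats the same window.

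**The concern.** A ± window is harmless for a clinic visit or a blood draw. Applied to drugs, its early side eats into the part of the cycle in which no lenalidomide or ixazomib is given. From cycle 3 the early allowance is 7 days, exactly the length of the lenalidomide rest. The protocol therefore asks for a rest week and also permits a start that removes it.

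What is at stake is patient safety and consistent dosing across sites. A site that follows the window to the letter could give two 21-day lenalidomide courses back to back without a protocol deviation.

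**Working it through.** **Inputs**
- Cycle length: 28 days (Sections 1.4 and 5.1).
- Last lenalidomide day: 21 (Sections 5.2.2 and 8.2.7). Last ixazomib day: 15 (Section 8.1.7). Last dexamethasone day in induction: 22 (Section 5.2.3).
- Early allowance: 3 days for the start of cycle 2, 7 days for the starts of cycles 3-24.

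**Formulas**, for a start *k* days early after an on-time Day 1
- Interval between Day 1s = 28 − *k*
- Lenalidomide rest = (28 − *k*) − 21 = 7 − *k*
- Ixazomib gap, Day 15 to next Day 1 = 14 − *k*
- Dose-intensity ratio over that interval = 28 / (28 − *k*)

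| Start | Interval (days) | Lenalidomide rest (days) | Ixazomib gap (days) | Intensity ratio |
|---|---|---|---|---|
| On time (the plan) | 28 | 7 | 14 | 1.00 |
| 3 days early | 25 | 4 | 11 | 28/25 = 1.12 |
| 7 days early | 21 | 0 | 7 | 28/21 = 1.33 |

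The first row reproduces the planned schedule.

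**In milligrams, 7 days early, at full dose**
- Lenalidomide, induction: 21 × 25 = 525 mg; 525/3 = 175 mg/week against 525/4 = 131.25 planned.
- Lenalidomide, maintenance: 21 × 15 = 315 mg; 315/3 = 105 mg/week against 315/4 = 78.75 planned. This is still below the planned induction rate.
- Ixazomib: 3 × 4 = 12 mg; 12/3 = 4.0 mg/week against 12/4 = 3.0 planned. Seven days is the normal spacing within a cycle, so what is lost is the extra week off.
- Dexamethasone, induction: with a 21-day interval, Day 22 of one cycle is Day 1 of the next. The text does not say how to handle the shared day.

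**If the previous start was late.** The protocol does not say what its specified dates are counted from. Suppose they are fixed from Cycle 1 Day 1.
- A start 7 days late followed by an on-time start leaves 28 − 7 = 21 days, so the rest is again 0.
- A start 7 days late followed by one 7 days early leaves 28 − 14 = 14 days. That is shorter than the 21-day lenalidomide course, so two courses would overlap by 7 days.

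Changing the window to delay-only would therefore not be enough. The interval has to be counted from the previous actual Day 1.

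**The case against.** **A sensible reader would keep the rest week.** The cycle is defined as 28 consecutive days, Section 5.2.2 states the rest in words for cycles 1-9, and footnote 3 presents the window as a scheduling allowance. Sections 5.3 and 6.1 speak of delays and never of early starts. This shows what was probably intended. It does not settle the text: Section 10 names medications, and Section 5.2.2 puts the rest and the two-sided window in the same paragraph without saying which prevails.

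**Other controls limit exposure.** A new induction cycle requires recovery of ANC, platelets and non-hematologic toxicity (Section 6.1), and low Day 1 counts hold both drugs (Table 11). Lenalidomide is supplied one cycle at a time (Section 8.2.8), as is ixazomib in induction (Sections 8.1.3 and 8.1.6). These lower the risk, and that part of the objection stands. None sets an interval, however, and Section 6.1 has no lenalidomide start criteria in either phase. If the every-3-cycles option is used in maintenance, visits fall at cycles 10, 13, 16, 19 and 22. Ten of the 15 maintenance cycles then start under local guidelines, and the patient may hold a 3-month ixazomib supply.

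**Two stronger readings that the documents do not support**
- *An early start inside the window is a reportable lenalidomide overdose.* The overdose text in Section 7.8 includes dosing more often than the required schedule. But the required schedule can be read to include the window, and the same text gives a second definition that requires the dose to be excessive and medically important. The protocol leaves the question open. This is a secondary ambiguity, not an established conflict.
- *The whole course could be compressed.* If each of the 22 starts from cycle 3 came 7 days early, counted from the previous start, 24 × 28 = 672 days would become 672 − 22 × 7 = 518. That is hard to reconcile with the 24 months of treatment stated in Sections 1.4 and 5.1, and it would need the start criteria to be met early every time they apply. It is not a fair measure of the problem.

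**Conclusion.** The window is wrong as written; the point is minor. One permitted early start can reduce the lenalidomide rest from 7 days to 0, halve the ixazomib gap from 14 days to 7, and raise the dose intensity of both drugs by 33% over that interval. The smaller window for cycle 2 has the same fault: 4 rest days and 12% higher intensity.

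These figures assume full use of the early allowance after an on-time Day 1, with all scheduled doses taken. If dates are fixed from Cycle 1 Day 1, a preceding late start can make the interval shorter still. How often early starts would occur is not known, and the documents show no harm from them.

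Alpha, power, sample size and the primary estimate are not affected. The calculation in Section 13.1 rests on 53 eligible patients and 2-year progression-free rates of 50% and 70%, none of which depends on this window.

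**What to change.** Keep the ± windows for visits and assessments. For dosing, add one sentence to Sections 1.4, 5.1, 5.2.2 and 10 and to footnote 3 of the Study Calendar:

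> A new cycle of study drugs may not start earlier than 28 days after the actual Day 1 of the previous cycle, so that at least 7 days off lenalidomide are kept; late starts within +3 days (cycle 2) or +7 days (cycles 3-24) are allowed.

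The longer delays already allowed in Sections 5.3 and 6.1 can stay as they are. From cycle 3, in-window intervals then run from 28 to 35 days, lenalidomide rest from 7 to 14 days, and the scheduled ixazomib gap from 14 to 21 days. The dexamethasone overlap no longer arises, and an in-window start can no longer be read as too frequent dosing. Late make-up of a missed ixazomib dose under the 72-hour rule in Section 5.2.1 is a separate matter and is unchanged.

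**Cost.** Scheduling is less flexible, and some early starts will be recorded as deviations. Late starts can accumulate because each is counted from the previous actual Day 1. At the limit this adds 3 + 22 × 7 = 157 days, for 672 + 157 = 829 days in all. That would run past the 2-year landmark and move the end-of-treatment imaging with it. This is an extreme that needs every start to be as late as allowed.
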